6.3 INTERCURRENT EVENTS

The intercurrent events (ICE) of interest in this trial are:

- Death, with date and time of death as recorded on the EoS / Adverse Event eCRF pages.
- Treatment discontinuation, with date/time of last IMP intake as the date/time of the intercurrent event,
 - due to reasons related to IMP (any treatment discontinuation with reason “Perceived lack of efficacy” or reason “Adverse Event”, with the corresponding AE indicated as being related to study treatment),
 - due to reasons unrelated to IMP (all other reasons).
- Change in (pharmacological or non-pharmacological) antidepressant treatment:
 - Introduction of further antidepressant treatments: Cases will be identified via manual review. Final decisions will be made during the last RPM. All identified cases will be documented in the Clinical Trial Analysis Decision Log [ref. 9.3].
 - Change in existing background psychotherapy (stop of baseline psychotherapy, start of new psychotherapy after first IMP intake, change in frequency and/or session settings of baseline psychotherapy), with date/time defined as the

minimum of the end date/time of respective psychotherapy recorded at baseline
and start date/time of a newly initiated psychotherapy

CTP Section 7.2.2:

The primary treatment effect of interest is the effect obtained at the primary time point if the participant had stayed on randomised IMP, i.e. cases of treatment discontinuation, regardless of reason [(including death)], will be handled using a hypothetical approach [...]. Data collected after treatment discontinuation + [residual effect period (JREP)] will be censored and will not be included in the analysis.

Changes in antidepressant treatment [including changes in background psychotherapies] will be disregarded in the primary analysis of treatment effect, i.e. they will be handled using the treatment policy approach as defined in ICH E9(R1).

[figure not shown]

Table 2: Strategies for handling ICEs

ICE	Primary	
Death	Hypothetical	
Treatment discontinuation related to IMP	Hypothetical	
Treatment discontinuation unrelated to IMP	Hypothetical	
Change in pharmacological or non-pharmacological antidepressant treatment	Treatment policy	
Analysis flags to be used (REP = 8 days)	ANL01FL='Y'	

Each analysis will reference the strategy for handling ICEs that was used.

For the handling of efficacy assessments after the REP within the different strategies, please see [Section 6.6.4](#).

6.4 PARTICIPANT SETS ANALYSED

CTP Section 7.2.1:

Statistical analyses will be based on the following main analysis sets:

- Treated set (TS):

The TS includes all participants who were randomized and treated with the IMP. The TS will be used for safety and most of the efficacy analyses. Safety analyses will be conducted using actual treatment received. [Participants to whom medication from kits with varying medication was dispensed will be included in the safety analyses with their randomised treatment. For these participants as well as for participants who received medication different from the one assigned for the entire trial, additional listings will be created to support review of safety-related data in relation to the actual treatment received.] For efficacy analyses, treatment assignment will be as randomised, unless specified otherwise.

- Primary analysis set (PAS)

The PAS comprises all randomised participants who received at least one dose of IMP during the trial and had a baseline MADRS total score ≥ 24 . The primary analysis [and all MADRS-based analyses] will be performed on the PAS and will be based on assigned treatment.

Additionally, for participant disposition, the following analysis sets will be considered:

- Screened set (SCS):

The SCS includes all participants who have signed informed consent.

- Randomised set (RS):

The RS includes all randomised participants, whether treated or not.

For analyses of disposition, iPDs, demographic data and baseline characteristics based on the SCS, RS or PAS, the treatment assignment will be as randomised; respective analyses based on the TS will be conducted using actual treatment received.

Table 3: Participant Sets Analysed

Class of endpoint	Participant set				
	SCS	RS	TS	PAS	
Disposition	X				
iPDs		X			
Demographic data/baseline characteristics			X	X	
Primary endpoint			X	X	
Treatment exposure			X		
Other safety parameters			X		

6.6 HANDLING OF MISSING DATA AND OUTLIERS

6.6.1 Questionnaire-based data

As all questionnaires except for MADRS and HDRS-17 are captured electronically, it is expected that, for a time point, the questionnaire is either fully completed or completely missing – missing single items or multiple answers for one item are not expected for the electronically captured questionnaires. In the unlikely case that such events occur, [REDACTED] missing values will not be imputed and summary scores derived from these items will be missing.

6.6.1.1 MADRS Total Score [REDACTED]

In case a single item of the questionnaire is missing at a time point, the total score will be set to missing for this time point, too. [REDACTED]

Considering analysis of change from baseline in MADRS total score [REDACTED] the MMRM used for these analyses implicitly imputes missing data, assuming they are missing at random.

6.6.1.2 Other Questionnaire-based Endpoints

In analysis of endpoints based on MMRM, the analysis implicitly imputes missing data, assuming they are missing at random. No other imputation of missing data will be performed for these endpoints.

6.6.2 AE [REDACTED]

Missing or incomplete AE dates are imputed according to Boehringer Ingelheim standards [[ref 9.10](#)].

[REDACTED]

[REDACTED]

6.6.4 Handling of efficacy assessments after REP

The primary characterisation of efficacy will be on treatment which will assume all participants took randomised treatment for the duration of the trial.

Consequently, analyses using the primary analysis approach, with the primary strategy for handling ICEs (see [Section 6.3](#)) will be on treatment, i.e. data observed after last IMP intake + REP will generally be excluded from these analyses.

[REDACTED]

6.7 BASELINE, TIME WINDOWS AND CALCULATED VISITS

In general, the last non-missing value within the pre-dose time window will be defined as baseline.

If the time of an assessment/measurement (except for ECG) was not captured, and it was on the same day IMP administration started, it will be assumed that it was taken prior to first IMP; for ECG, which was planned to be performed after first IMP intake at Visit 2 as per CTP, such assessments will not be considered for baseline.

Time windows will be used as described in the following tables, in order to assign data to the relevant visit/time point based on the actual date/time of the assessment. Data will then be analysed using these assigned analysis visits/time points in the statistical tables. Assignment of values to time windows is thereby in general irrespective of the analysis phase (Screening, On-treatment, or Follow-up) they fall into. Consequently, if analyses require participants with at least one non-missing post-baseline value to be included, then this refers to available values within the analysis time windows and for the relevant analysis phase (if applicable).

However, in the listings, all assessments performed will be displayed (even if outside the analysis time windows), along with the assigned analysis visits/time points (if applicable).

Analysis time windows for different assessments are defined in [Table 4](#), [Table 5](#), [Table 6](#), and [Table 7](#), with Day 1 referring to the day of first IMP intake in all cases.

If after assignment of analysis time windows, two or more values fall within the same post-dose analysis time window, then the measurement closest to the planned time point will be used for analysis. In case two measurements are equidistant from the planned time point, then the later one will be picked. For Day 1 (post-dose for ECG), Day 8, Week 2, Week 4, and Week 6, in the above, on-treatment values will generally be prioritized over follow-up values. I.e. if there is one or more on-treatment values in the respective time window, the analysis value will be selected from the available on-treatment values. Follow-up values will only be considered if there are no on-treatment values within the respective time window.

Consequently, if statements are made regarding ‘all post-baseline values to be included’ for an analysis considering analysis time windows, then this includes only the respectively flagged values within the time windows (and analysis phase).

Adherence to time windows will be checked at the last RPM at the latest. Any handling of assessments differing from the described general rules will be documented in the Clinical Trial Analysis Decision Log [[ref. 9.3](#)].

Table 4: Analysis time windows for MADRS, [REDACTED]

Assessments	Label	Target day	Analysis time windows	
			Start	End
MADRS, [REDACTED] [REDACTED]	Pre-dose	1		Day 1, prior to IMP
	Day 8	8	Day 6	Day 9
	Week 2	15	Day 11	Day 22
	Week 4	29	Day 23	Day 36
	Week 6	43	Day 37	
[REDACTED]				
[REDACTED]				

[figure not shown]
Table 5: Analysis time windows for [REDACTED], Safety lab (blood/urine), and vitals

Assessments	Label	Target day	Analysis time windows	
			Start	End
[REDACTED], Safety lab (blood/urine/drug screening), vitals	Pre-dose	1	Day -35	Day 1, prior to IMP
	Day 8	8	Day 6	Day 10

Assessments	Label	Target day	Analysis time windows	
			Start	End
(excluding weight, BMI, height)	Week 2	15	Day 11	Day 22
	Week 4	29	Day 23	Day 36
	Week 6	43	Day 37	Day 47
	Week 8	51	Day 48	
Weight, BMI	Pre-dose	1	Day -35	Day 1, prior to IMP
	Week 6	43	Day 37	Day 47
Height	Pre-dose	1		Day 1, prior to IMP

Table 6: Analysis time windows for ECG

[figure not shown]
Assessments	Label	Target day	Analysis time windows	
			Start	End
ECG	Pre-dose	1	Day -35	Day 1, prior to IMP
	Day 1	1	Day 1, post IMP	Day 1, 23:59
	Day 8	8	Day 6	Day 10
	Week 4	29	Day 23	Day 36
	Week 6	43	Day 37	Day 47
	Week 8	51	Day 48	

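### SAP Table 4 leaves Day 10 in no MADRS analysis window, so a rating on that day is listed but not analysed (minor)

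*SAP*

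**What the plan says.** SAP Section 6.7 uses analysis windows "in order to assign data to the relevant visit/time point based on the actual date/time of the assessment". The nominal visit does not decide the time point.

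- Table 4 (MADRS and redacted scales) has "Day 8 8 Day 6 Day 9", followed by "Week 2 15 Day 11 Day 22". The columns are label, target day, first day and last day. Week 4 is Day 23 to 36, and Week 6 is Day 37 onwards.
- Tables 5 (safety laboratory, vital signs) and 6 (ECG) have "Day 8 8 Day 6 Day 10" for the same time point.

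Where an analysis needs at least one post-baseline value, the section says "then this refers to available values within the analysis time windows and for the relevant analysis phase". It also restricts any reference to all post-baseline values to the flagged in-window ones. Values outside the windows still appear in listings. If two values share a window, the one closest to the target day is used. Adherence to the windows is checked by the last Report Planning Meeting, and "Any handling of assessments differing from the described general rules will be documented in the Clinical Trial Analysis Decision Log".

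SAP Section 7.5.1 fits the primary MMRM to participants with a baseline and at least one post-baseline MADRS value. It reports adjusted means, differences to placebo, confidence intervals and p-values at each time point, which includes Day 8.

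**The concern.** Day 10 is the only day between the first window and the end of follow-up that has no MADRS time point. SAP Section 6.7 gives no reason for this, and the companion tables treat the same day as part of the Day 8 time point. A rating made on Day 10 would be dropped from the model while laboratory, vital-sign and ECG values from that day were kept.

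Ratings on Day 10 are foreseeable. Protocol Section 6.1 asks for missed appointments to be rescheduled where possible. Protocol Section 4.1.4 supplies 7 + 3 = 10 treatment days at Visit 2, so supply reaches Day 10. Protocol Section 3.3.4.1 asks for an end-of-treatment visit soon after permanent discontinuation, ideally 24 hours after the last dose, and such a visit can fall on any day.

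A Day 10 rating after a last dose on Day 9 is well inside the 8-day residual effect period (SAP Section 6.1). It is on-treatment data, which the primary strategy in SAP Sections 6.3 and 6.6.4 means to keep. The window removes it for a reason unrelated to the estimand.

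**Working it through.** **Inputs.** Windows and targets come from SAP Section 6.7, Tables 4 to 6. The residual effect period of 8 days comes from SAP Section 6.1.

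**Step 1: coverage.** Each study day after Day 1 was checked against the windows.

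| Assessment | Windows (days) | Days in no window | Day 10 goes to |
|---|---|---|---|
| MADRS, Table 4 | 6–9, 11–22, 23–36, 37 on | 2–5, **10** | none |
| Laboratory and vital signs, Table 5 | 6–10, 11–22, 23–36, 37–47, 48 on | 2–5 | Day 8 |
| ECG, Table 6 | 6–10, 23–36, 37–47, 48 on | 2–5, 11–22 | Day 8 |

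The ECG gap on Days 11–22 has an explanation: Table 6 has no Week 2 time point. The MADRS gap on Day 10 has none. The other MADRS joins are contiguous (22/23 and 36/37).

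**Step 2: which time point Day 10 is closer to.** Distance to the Day 8 target is 10 − 8 = 2 days. Distance to the Week 2 target is 15 − 10 = 5 days. As written, the Day 8 window accepts a rating 8 − 6 = 2 days early but only 9 − 8 = 1 day late. The Week 2 window accepts one 22 − 15 = 7 days late. Ending the Day 8 window on Day 10 makes it 2 days either side of target.

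**Step 3: effect of the change.** With a Day 8 window of 6–10, the uncovered MADRS days become 2–5, the same as for laboratory and vital signs. Since Week 2 starts on Day 11, nothing overlaps.

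**Step 4: who is affected.**

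- Rating on Day 10 and another on Days 6–9: usually no change. A rating on Day 8, for example, is closer to target and is used under either rule. The one exception is a rating on Day 6 and another on Day 10. These are equidistant, so the later would be picked, but a Day 8 value exists either way.
- Rating on Day 10 and none on Days 6–9: the Day 8 value is lost.
- As above, and no other in-window on-treatment rating: the participant drops out of the primary model. With a last dose on Day 9, the on-treatment phase runs to about 9 + 8 = Day 17, so a Day 15 rating during continued follow-up would keep the participant in.

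**Step 5: primary result.** Week 6 uses ratings from Day 37 on. A lost Day 8 value reaches the Week 6 estimate only through the repeated-measures correlation, and hardly at all when the Week 6 score is observed. The power calculation in protocol Section 7.5 rests on Week 6 change in 180 evaluable participants with SD 10. No window enters it, so sample size and power do not change.

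**The case against.** The best case for leaving the table alone has four parts.

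1. **Contiguity is not a stated rule.** Every table leaves Days 2–5 uncovered, and Tables 4 and 5 differ elsewhere: the MADRS pre-dose window has no start and its Week 6 window has no end. The boundaries do not strictly follow the nearest target either. Day 11 is 3 days from Day 8 and 4 from Day 15, yet it goes to Week 2. This stands to the extent that the gap is certain while the intention behind it is inferred.
2. **There is an exception route.** The Report Planning Meeting can admit a Day 10 value and log the decision. This softens the problem, but it is a case-by-case departure made after the values exist. A pre-specified window is cleaner.
3. **The affected group is narrow,** as Step 4 shows. This stands.
4. **Little depends on Day 8.** The only endpoint visible in the documents is Week 6, there are no secondary endpoints, and SAP Section 7 makes every p-value other than the primary dose-response test nominal. This also stands.

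A reader might infer that the SAP throws away a valid rating. The documents do not support that. The Visit 3 visit window is not visible in the supplied schedule, so Day 10 may be an in-window or a late visit, and the value remains in the listings. A reader might also infer that the gap damages the evidence for rapid onset. The protocol does describe speed as the drug's potential advantage, but no visible endpoint or decision rule uses the Day 8 result.

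**Conclusion.** The gap is real and sits in the current SAP text. Under the SAP's own rules, a Day 10 MADRS rating is kept out of the MMRM and the summary tables unless it is individually rescued. The consequence is minor: a loss of Day 8 information for participants with no rating on Days 6–9, and a rare loss of a participant from the primary model.

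The number affected cannot be determined from the documents. If one assumed that 2% to 5% of 180 participants were rated on Day 10, the count would be 0.02 × 180 = 3.6 to 0.05 × 180 = 9. That share has no support in the documents, and the count also assumes that none of them had a Day 6–9 rating. It should not be read as an estimate.

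The effect on the Week 6 estimate is expected to be very small. The conclusion assumes that the redacted rows of Table 4, which follow a complete MADRS sequence, do not cover Day 10 for MADRS.

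**What to change.** Before treatment information is released, change the last day of the Day 8 window in SAP Table 4 from Day 9 to Day 10, as in Tables 5 and 6. Alternatively, keep the gap and state why Day 10 is excluded. Starting Week 2 on Day 10 would also close it, but Day 10 lies nearer to the Day 8 target.

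The cost is one table cell and one programming constant. The redacted scales that share the Table 4 row would change as well, so the sponsor should confirm that Day 10 suits them before making the edit.

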7. PLANNED ANALYSIS

For End-Of-Text tables, the set of summary statistics is:

N	number of non-missing observations
Mean	arithmetic mean
SD	standard deviation
Min	minimum
Q1	1 st quartile
Median	median
Q3	3 rd quartile
Max	maximum

Tabulations of frequencies for categorical data will include all possible categories and will display the number of observations in a category as well as the percentage (%) relative to the

respective treatment group (unless otherwise specified, all participants in the respective participant set whether they have non-missing values or not).

The precision for percentages should be one decimal point. The category missing will be displayed only if there are actually missing values.

Any p-value presented will be from two-sided tests and confidence intervals (CI) will be two-sided 95% CI, unless otherwise specified. Apart from the p-values from the primary test for a flat dose response relationship on change from baseline in MADRS total score at Week 6, all p-value presented will be considered descriptive (nominal) in nature.

Analyses performed by treatment group will consider the following treatment groups:

- Placebo,
- 5 mg BI,
- 10 mg BI,
- 20 mg BI,
- BI total (where applicable), and
- Total (where applicable).

Thereby, summary tables of disposition, demographics and other baseline characteristics data, as well as descriptive summaries of safety data, including treatment compliance and treatment exposure data, and descriptive summaries of efficacy data will in general include a BI total and a total column.

For model-based analyses, unless stated otherwise, the actual strata “number of antidepressants used for the current episode” (0 vs 1) and “baseline MADRS total score” (< 24 vs ≥ 24) as documented in the eCRF will be used, as applicable. If erroneous data was documented and used for randomisation in IRT, this will be described accordingly – but these erroneous data will in general not be used for the model-based analyses.

7.1 DEMOGRAPHIC AND OTHER BASELINE CHARACTERISTICS

Only descriptive statistics are planned for this section of the report. Unless otherwise stated, summaries will be provided for the TS.

Substance use data will be summarised by visit, using the number of patients at each visit as the denominator for percentage calculation.

A summary of suicidal ideation and suicidal behaviour data from the C-SSRS as collected at screening will be provided.

Furthermore, demographic data, baseline conditions, and additional medical history of study indication will be displayed for the PAS, as well as by subgroup for the subgroups defined in [Section 6.5](#), also based on the PAS. An overview of the number of patients in the different subgroups will also be provided for the PAS.

Additionally, a listing of participants who were re-screened, including reason for initial screen failure and status following the final screening (i.e. screen failed or randomized) will be provided.

7.2 CONCOMITANT DISEASES AND MEDICATION

Baseline conditions (ongoing at the date of informed consent) / medical history (not ongoing after date of informed consent) will be coded using the current Medical Dictionary for Regulatory Activities (MedDRA) version in use at Boehringer Ingelheim at the time of database lock (DBL). They will be summarised descriptively, separately by MedDRA system organ class (SOC) and preferred term (PT).

Concomitant medications will be coded using the current World Health Organization Drug Dictionary (WHO-DD) version in use at Boehringer Ingelheim at the time of database lock.

Concomitant non-drug therapies will be coded using the current MedDRA version in use at BI at the time of DBL.

A medication/non-drug therapy will be considered concomitant to treatment, if

- it is ongoing at the time of first trial drug administration, or
- starts within the on-treatment analysis phase of the respective treatment (see [Section 6.1](#) for a definition of treatments and analysis phases).

A medication/non-drug therapy will be considered concomitant to follow-up, if

- it is ongoing at the start of the follow-up analysis phase, or
- starts within the follow-up analysis phase (see [Section 6.1](#) for a definition of analysis phases).

In case of missing or incomplete date/time information, a medication/non-drug therapy will be considered concomitant to treatment and follow-up, unless the available information (including the flag indicating that a medication/non-drug therapy was ongoing at the end of study) clearly indicates that the medication/non-drug therapy was not concomitant to treatment or follow-up, respectively.

Concomitant medications (concomitant to treatment, and concomitant to treatment or follow-up) will be summarised by Anatomical Therapeutic Chemical (ATC) classification and preferred name (PN), using the ATC3 levels for the TS. These summaries will be sorted alphabetically by ATC class, and by decreasing frequency in “Total”-column within ATC class.

Medications concomitant to treatment will additionally be displayed for the PAS, as well as by subgroup for the subgroups defined in [Section 6.5](#), also based on the PAS.

Psychotherapy for the primary indication (MDD) at baseline (i.e. ongoing at time of first IMP intake) will be summarised descriptively, via frequency tables for frequency and session setting for the TS. The number and percentage of participants with on-treatment changes in psychotherapy will also be provided within the overview of ICE.

Other non-drug therapy data will only be listed.

7.3 TREATMENT COMPLIANCE

Only descriptive statistics are planned for this section of the report. Summaries will be provided by visit, based on the number of patients per visit for the TS.

7.4 INTERCURRENT EVENTS

Intercurrent events will be summarised as number and percentage of participants with each ICE. By-participant-listings of all ICEs will be created.

7.5 PRIMARY OBJECTIVE ANALYSIS

7.5.1 Main analysis

CTP Section 7.2.3.1:

[...] *the primary endpoint is the change from baseline to Week 6 in MADRS total score.*

[MCPMod is used for the primary analysis of the primary endpoint – to test the null hypothesis that there is a flat dose response curve comparing placebo and the BI 1569912 dose groups on the primary endpoint.]

MCPMod (multiple comparison and modelling techniques) [ref. 9.17] is used to evaluate several possible dose response models (patterns). As a basis for the MCPMod analysis, a restricted maximum likelihood estimation (REML) based on a mixed model for repeated measures (MMRM) analysis will be used to generate covariate adjusted estimates of mean change from baseline in MADRS total score at Week 6 and associated covariance matrices. The model will include fixed categorical effects of treatment at each visit and number of antidepressant treatments taken for current episode (0 versus 1), and fixed continuous effects of baseline MADRS total score at each visit.

The Kenward-Roger approximation will be used to estimate denominator degrees of freedom and adjust standard errors (SEs). Least-squares mean estimates per dose group and differences to placebo at each time point, corresponding two-sided 95% CIs and p-values will be presented in tables. Further, for the differences to placebo at each time point, standardized effect sizes will be calculated based on the results/estimates of this analysis (standardized effect size = (adjusted mean difference in change from baseline between treatment groups) / (SE / sqrt(1/n + 1/m)), where n and m are the number of participants in the respective treatment group).

Additionally, adjusted means and corresponding SEs will be presented graphically over time.

For the MMRM, an unstructured covariance matrix will be assumed. In case of non-convergence the following steps will be taken (in that order) to overcome convergence issues:

1. Add the 'singular=1e-10' option in the model statement
(This raises the threshold at which columns are declared linearly dependent (from typically 1e-12).)
2. Set 'maxiter=100' in the Proc Mixed statement
(This increases the number of convergence iterations used from a default of 50.)
3. Set 'scoring=4' to specify use of the Fisher scoring algorithm in the first 4 iterations.
4. Include the statement 'performance nothread'
(This removes multi-threading, possibly improving stability, but may also slow down calculations.)
5. Provide starting values for covariance parameters using a 'parms' statement.

6. Should none of the previous methods work, the covariance matrix will be changed from unstructured to Toeplitz with heterogeneous variances (TOEPH). Should this also not converge, a standard Toeplitz matrix (TOEP) will be fitted. Finally, if convergence still does not occur, then an order-1 autoregressive matrix (AR(1)) will be fitted.

CTP Section 7.2.3.1:

Participants from the PAS with a baseline and at least one post-baseline value with their MADRS values of all post-baseline visits, will be included in the model, according to the considered strategy for handling intercurrent events [(see Section 6.3) Note that the MMRM automatically excludes observations of participants without a baseline and at least one post-baseline value from analysis.]

The primary treatment comparisons will be the contrasts between each BI 1569912 treatment arm and placebo at Week 6.

The dose-response relationship of these estimates from the MMRM will then be analysed using MCPMod. Thereby, several possible dose response models (patterns) will be evaluated (while keeping full control of the type I error at 10%, one-sided) to identify the best-fitting model or subset of models.

A monotone dose-response relationship is assumed. For the PoCC testing and for the sample size calculations the following model assumptions (Table 8) and resulting graphs [Figure 1] have been selected to cover both the plausible and a diverse range of potential dose response patterns.

Table 8: Dose response pattern assumptions and rationale

Model	Description
Linear	Linear dose response
E_{max1}	50% of the maximum effect (ED₅₀) is achieved at the 5 mg dose
E_{max2}	95% of the maximum effect (ED₉₅) is achieved at the 10 mg dose
Exponential	5% of the maximum effect is achieved at the 5 mg dose, i.e. high effect only at a high dose
Sigmoid E_{max}	20% of the maximum effect (ED₂₀) is achieved at the 5 mg dose, 80% of the maximum effect (ED₈₀) is achieved at the 10 mg dose, i.e. effect of 5 mg and 10 mg are further apart (fixed hill parameter h=4)

[figure not shown]

Figure 1: Shape and considered dose response patterns for the MCPMod analysis

The optimal contrasts corresponding to the candidate models [are shown in the following table (see [Section 10.5](#) for the R code used for the calculation)].

Table 9: Contrast coefficients

[figure not shown]
	Contrast coefficients			
Model	Placebo	5 mg BI	10 mg BI	20 mg BI
Linear	0.639	0.145	-0.029	-0.755
Emax1	0.755	0.029	-0.145	-0.639
Emax2	0.840	-0.156	-0.208	-0.476
Exponential	0.487	0.211	0.138	-0.836
Sigmoid Emax	0.683	0.200	-0.212	-0.670

[figure not shown]
[figure not shown]
For the final evaluation, these contrasts will be updated using the expected model means from the candidate set and the estimated variance-covariance matrix extracted from the MMRM model.

A non-flat dose response is established if at least one dose response pattern is statistically significant, rejecting the null hypothesis of a flat dose response relationship on change from baseline in MADRS total score at Week 6 jointly for each of the candidate dose response models, with a contrast test controlled for the family-wise type I error rate at a one-sided $\alpha = 10\%$.

If a non-flat dose response is established, the statistically significant (i.e. best fitting) model(s) from the above candidate set are refitted to the data to generate new estimates for all model parameters. The dose-response curve is then obtained via model averaging across the significant models based on Akaike Information Criteria (AIC). [The predicted change from baseline in MADRS total score at Week 6 and difference to Placebo based on data fit via MCPMod to each model shape will be calculated for significant shapes.]

The target dose(s) for further clinical development can be estimated from each significant model by incorporating information on the minimum clinically relevant effect. The totality of evidence, including secondary and further efficacy and safety parameters, will be taken into account in the selection of dose(s) for pivotal studies.

[figure not shown]
